3.2 Exclusion Criteria

- Participants $<$ 18 years of age
- Pregnant women
- Cognitive impairment
- Participants with vertigo or other balance issues
- Participants unable to provide informed consent
- Non-English speaking individuals
- Participants who will not be wearing a CAM boot
- Participants unable/unwilling to perform upper body exercises and follow nutrition recommendations

3.3 Early Withdrawal of Subjects

3.3.1 Criteria for removal from study

Participants will be withdrawn from the study for safety reasons including severe adverse reactions, pregnancy, failure of subject to adhere to protocol requirements, or subject consent withdrawal.

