3.0 Inclusion and Exclusion Criteria

3.1 Inclusion Criteria

- Participants \geq 18 years of age
- Sex: male or female
- Participants prescribed a CAM boot as standard of care from the principal investigator's practice
- Participants willing to have weight measured at the clinic site at time of enrollment and at final visit
- Participants willing to have blood drawn for Albumin level at beginning and end of study
- Participant is able to provide voluntary, written informed consent
- Participant, in the opinion of the clinical investigator, is able to understand the clinical investigation and is willing to perform all study procedures and follow-up visits.
- Fluent in written and spoken English

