3.3.2 Follow-up for withdrawn subjects

If a participant is withdrawn from the study, data collection will be terminated from that time point forward. All prior data collected will be included in the analysis. These participants will not be replaced, but instead more participants may need to be enrolled. These new data will be recorded and analyzed as would any other new enrollee.

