7.2 Study Procedures

7.2.1 Visit 1 - Enrollment

Patients will be given information about the study and asked to participate. If eligible, based on inclusion and exclusion criteria, informed consent will be obtained at the time of the screening visit and the patient will be enrolled in the study.

After obtaining informed consent, patients will be randomized to one of two groups. A sealed envelope will be drawn containing one of the two treatment groups. This study will not be blinded as patients would easily be able to detect which treatment group they are randomized too.

- **Group 1 (Control)** – Patients are prescribed CAM boot as part of their standard of care treatment. No nutritional and exercise information will be provided.

Patients will be given an Albumin lab test request for blood (8mL) to be drawn at the PSHMC Clinical Laboratories at time of enrollment (+/5 days) and again at their final visit (+/- 5 days). Patients with abnormal lab testing results will be referred to their primary care physician for further evaluation and management.

Patient's height and weight will be measured and recorded using a scale already located in the practice site clinic.

- **Group 2 (Intervention)** – Patients are prescribed CAM boot as part of their standard of care treatment and provided nutritional/exercise information at the time the CAM boot is dispensed.

Patients will be provided upper body physical exercises consisting of seated upper body physical exercises (with or without weights) to include chest press, chest pulls, butterfly wings, front raise, upright row, biceps curls, overhead press and triceps extension exercises (Appendix 1). Patient is instructed to perform these exercises three days per week and each exercise three times per session (or to the best of his/her ability).

Patients will be provided nutritional guidelines (Appendix 2) which is intended as a guide for adults who want to follow a healthful eating pattern.

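### Withdrawal for non-adherence ends data collection, so a randomised participant withdrawn before Visit 2 has no primary outcome, and losses could differ between arms

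*Combined protocol and SAP*

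**What the plan says.** - **Section 3.3.1** gives the reasons for which participants will be withdrawn. Besides severe adverse reactions and pregnancy, these are "failure of subject to adhere to protocol requirements, or subject consent withdrawal". The protocol requirements in question are not defined. The sentence opens by referring to safety reasons, so it could be read as covering only safety-related non-adherence.
- **Section 3.3.2** applies to every withdrawal, whatever the reason: "If a participant is withdrawn from the study, data collection will be terminated from that time point forward". It adds "All prior data collected will be included in the analysis" and "These participants will not be replaced, but instead more participants may need to be enrolled".
- **Sections 1.2, 7.2 and 7.3** make the primary endpoint the weight change when the boot is no longer required. Weight is measured at Visit 1 and Visit 2, and those are the only two visits.
- **Sections 7.1 and 7.2.1** give exercise and nutrition material to Group 2 only. The allocation is not blinded.
- **Section 9.2** specifies a two-sample t-test, or a Wilcoxon Mann Whitney test if the outcome is not normal. It names no analysis population and no approach to missing final weights. Section 9.1 makes no allowance for loss.

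**The concern.** The objective in section 1.1 concerns the effect of providing information when the boot is dispensed. That calls for comparing everyone randomised, whatever they later did with the information. A rule that removes non-adherent participants before their outcome is measured moves the comparison towards people who comply.

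If removal falls mainly on Group 2, and non-adherent people tend to gain more weight, the remaining Group 2 participants look better than the arm as a whole. Final weights that were never taken cannot be recovered. The trial's own data could not show the size or direction of the bias; a sensitivity analysis could only bound it. If numbers are not made up, even equal losses reduce power.

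**Working it through.** **Step 1: what the rule does.** Non-adherence leads to withdrawal (3.3.1), and withdrawal ends data collection (3.3.2). The only weight before Visit 2 is the baseline (7.2, 7.3). A participant withdrawn before Visit 2 therefore has no change score. Keeping prior data does not help, because a baseline weight alone gives no change. Enrolling more people restores numbers but not the outcomes of those already randomised.

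**Step 2: the plan's own power figure.** Inputs from section 9.1: 25 per group, difference 10 lb, SD 12 lb, two-sided 0.05. Noncentrality = 10 / (12 × √(1/25 + 1/25)) = 2.946 on 48 degrees of freedom. The noncentral t gives 82.3%, which agrees with the stated 82%.

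**Step 3: power if lost participants are not made up.** The formula is the same with the reduced group sizes. The losses are assumptions.

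| Outcomes available | Power for 10 lb |
|---|---|
| 25 v 25 | 82.3% |
| 25 v 24 | 81.5% |
| 25 v 23 | 80.6% |
| 25 v 20 | 77.5% |
| 23 v 23 | 78.9% |
| 20 v 20 | 72.9% |

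**Step 4: bias under no true effect.** Assume both arms have the same mean change and SD 12 lb, with 25 randomised per arm. A latent adherence score has correlation r with lower weight gain. The k least adherent are removed, which is the strongest form of the rule. Neither k nor r is in the documents.

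Let S(k) be the expected sum of the k largest of 25 standard normal values: S(1) = 1.965, S(2) = 3.490, S(5) = 6.724. With removals in Group 2 only, the false benefit is r × 12 × S(k) / (25 − k):

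- k = 1, r = 0.3: 3.6 × 1.965 / 24 = 0.295 lb
- k = 2, r = 0.3: 3.6 × 3.490 / 23 = 0.546 lb
- k = 5, r = 0.3: 3.6 × 6.724 / 20 = 1.210 lb

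For r = 0.5, replace 3.6 by 6. For 2 removed from Group 2 and 1 from control, r = 0.3 gives 3.6 × (3.490/23 − 1.965/24) = 0.25 lb.

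Type I error comes from simulating the pooled t-test, with at least 400,000 trials per setting (Monte Carlo standard error about 0.03 percentage points).

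| Removed (Group 2 v control) | Bias, r = 0.3 | Type I error, r = 0.3 | Bias, r = 0.5 | Type I error, r = 0.5 |
|---|---|---|---|---|
| 1 v 0 | 0.3 lb | 5.1% | 0.5 lb | 5.4% |
| 2 v 0 | 0.55 lb | 5.3% | 0.9 lb | 6.0% |
| 5 v 0 | 1.2 lb | 6.3% | 2.0 lb | 9.0% |
| 2 v 1 | 0.25 lb | 5.2% | 0.4 lb | 5.6% |

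There is no bias if r = 0, or if losses are equal and arise in the same way. At r = −0.3 the sign reverses: −0.3, −0.55 and −1.2 lb for 1, 2 and 5 removed.

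**The case against.** The strongest reply is that few people are likely to be removed before Visit 2, and that there is little in the documents to make removals unequal.

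- Eligibility in both arms requires that the participant "is willing to perform all study procedures and follow-up visits", and section 3.2 excludes "Participants unable/unwilling to perform upper body exercises and follow nutrition recommendations". Both apply before randomisation.
- The exercises are asked for only as far as the participant is able. The nutrition document is "intended as a guide for adults who want to follow a healthful eating pattern". The diary and dietary scale are optional.
- No study contact is scheduled between the visits. Non-adherence found only after the final weighing does no harm, since that weight is then prior data and is kept.
- The one requirement whose breach could show earlier without a contact is the enrolment albumin draw, which applies to both arms.
- The larger bias figures need 5 of 25 (20%) removed from one arm and none from the other, with removal ranked by adherence that staff could hardly observe.
- Section 9.2 already compares the two assigned groups, and no per-protocol set is defined.

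Most of this stands. It lowers the likelihood and size of the problem, and it is why unequal losses are only a possibility here. It does not remove the rule. Willingness at screening is not adherence afterwards, and because the requirements are undefined, removal is left to judgement in an unblinded trial. Reading 3.3.1 as limited to safety is strained, because consent withdrawal, which need not concern safety, is in the same list; if that reading was meant, the text should say so.

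**Conclusion.** The concern holds. Followed as written, the plan leaves anyone withdrawn for non-adherence before Visit 2 without a primary outcome, and section 9 does not say how that is handled. This follows from the text alone.

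The size does not. It depends on assumed losses and an assumed adherence–weight correlation. One or two removals from Group 2 would matter little against 10 lb; five could raise type I error to as much as 9.0% at r = 0.5. Whether losses would be unequal, and in which direction any bias would run, cannot be settled from the documents. The change is worth making because the loss cannot be repaired afterwards and is cheap to prevent.

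**What to change.** **Sections 3.3.1 and 3.3.2.** Define the protocol requirements and clarify whether the safety wording limits the list. State that non-adherence does not end data collection, and that the final weight is still recorded at the standard-of-care boot-removal visit unless consent for data collection is withdrawn. Say that keeping prior data does not mean the baseline weight stands in for the final one: that would enter a change of 0 lb, the value section 9.1 assumes for Group 2.

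**Section 9.2.** Make the primary analysis by randomised arm regardless of adherence. Report missing final weights by arm and reason. Add one sensitivity analysis that varies the assumed change of missing participants in each arm. As a scale, each missing Group 2 participant assumed to gain 10 lb more than Group 2 completers moves the difference by 10/25 = 0.4 lb. As a secondary matter, state how participants withdrawn for pregnancy or severe adverse reactions enter the analysis. A weight taken after pregnancy begins does not measure the effect of the boot or the information, so it could be treated as missing and covered by the sensitivity analysis.

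**Cost.** Two or three sentences in 3.3.1 and 3.3.2 and about four in 9.2, with a check that the consent wording matches. Sections 7.2.2 and 15.1 already treat the final visit as standard of care, so no visit is added. The downside is that the estimated effect may be smaller, because non-adherent participants stay in the analysis.

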3.3.2 Follow-up for withdrawn subjects

If a participant is withdrawn from the study, data collection will be terminated from that time point forward. All prior data collected will be included in the analysis. These participants will not be replaced, but instead more participants may need to be enrolled. These new data will be recorded and analyzed as would any other new enrollee.

4.0 Recruitment Methods

4.1 Identification / Recruitment of subjects

Adult patients presenting to the principal investigator's practice will be evaluated as part of standard of care. Those participants meeting eligibility requirements will be presented with the opportunity to participate in the research study by a member of the research team. These patients would normally be treated at the Penn State Hershey Medical Center and will be receiving the same care as those not enrolled in the study.

4.2 Recruitment materials – N/A

4.3 Eligibility/screening of subjects – N/A

5.0 Consent Process and Documentation

5.1 Consent Process

5.1.1 Obtaining Informed Consent

5.1.1.1 Timing and Location of Consent

Patients presenting to the principal investigator's practice site as part of their initial or routine evaluation will be given the opportunity to participate in the research study. Patients will be given information about the study and asked to participate. If eligible, based on inclusion and exclusion criteria, informed consent will be obtained at the time of the screening visit and the patient will be enrolled in the study.

5.1.1.2 Coercion or Undue Influence during Consent

Study procedures will be fully explained, voluntariness will be emphasized as well as the fact that no care will be denied regardless of the subjects decision. Participants will be given ample time to read and review the consent form on their own. All questions the patient may have will be answered and written consent will be obtained. A member of the research team will assist in the explanation and obtaining of the written consent. A copy of the signed consent will be given to the patient and another copy sent to Medical Records.

5.1.2 Waiver or alteration of the informed consent requirement - N/A

5.2 Consent Documentation

5.2.1 Written Documentation of Consent

A member of the research team will assist in the explanation and obtaining of the written consent. A copy of the signed consent will be given to the patient and another copy sent to Medical Records.

5.2.2 Waiver of Documentation of Consent - N/A

5.3 Consent – Other Considerations - N/A

5.3.1 Non-English Speaking Subjects - N/A

5.3.2 Cognitively Impaired Adults - N/A

5.3.2.1 Capability of Providing Consent - N/A

5.3.2.2 Adults Unable To Consent - N/A

5.3.2.3 Assent - N/A

5.3.3 Subjects who are not yet adults (infants, children, teenagers)

5.3.3.1 Parental Permission - N/A

5.3.3.1.1 Assent - N/A

6.0 HIPAA Research Authorization and/or Waiver or Alteration of Authorization

6.1 Authorization and/or Waiver or Alteration of Authorization for the Uses and Disclosures of PHI

Check all that apply:

- Authorization will be obtained and documented as part of the consent process.
- Partial waiver is requested for recruitment purposes only (*Check this box if patients' medical records will be accessed to determine eligibility before consent/authorization has been obtained*)
- Full waiver is requested for entire research study (*e.g., medical record review studies*)
- Alteration is requested to waive requirement for written documentation of authorization

6.2 Waiver or Alteration of Authorization for the Uses and **Disclosures** of PHI

6.2.1 Access, use or disclosure of PHI representing no more than a minimal risk to the privacy of the individual

6.2.1.1 Plan to protect PHI from improper use or disclosure

N/A: Authorization will be obtained and documented as part of the consent process.

6.2.1.2 Plan to destroy identifiers or a justification for retaining identifiers

N/A: Authorization will be obtained and documented as part of the consent process.

6.2.2 Explanation for why the research could not be practicably be conducted without access to and use of PHI

N/A: Authorization will be obtained and documented as part of the consent process.

6.2.3 Explanation for why the research could not practicably be conducted without the waiver or alteration of authorization

N/A: Authorization will be obtained and documented as part of the consent process.

6.3 Waiver or alteration of authorization statements of agreement

N/A: Authorization will be obtained and documented as part of the consent process.

7.0 Study Design and Procedures

7.1 Study Design

This will be a prospective, randomized trial with two groups.

Group 1 (Control) – Patients are prescribed CAM boot as part of their standard of care treatment. No nutritional and exercise information will be provided.

Group 2 (Intervention) – Patients are prescribed CAM boot as part of their standard of care treatment and provided nutritional/exercise information at the time the CAM boot is dispensed.

7.2 Study Procedures

7.2.1 Visit 1 - Enrollment

Patients will be given information about the study and asked to participate. If eligible, based on inclusion and exclusion criteria, informed consent will be obtained at the time of the screening visit and the patient will be enrolled in the study.

After obtaining informed consent, patients will be randomized to one of two groups. A sealed envelope will be drawn containing one of the two treatment groups. This study will not be blinded as patients would easily be able to detect which treatment group they are randomized too.

- **Group 1 (Control)** – Patients are prescribed CAM boot as part of their standard of care treatment. No nutritional and exercise information will be provided.

Patients will be given an Albumin lab test request for blood (8mL) to be drawn at the PSHMC Clinical Laboratories at time of enrollment (+/5 days) and again at their final visit (+/- 5 days). Patients with abnormal lab testing results will be referred to their primary care physician for further evaluation and management.

Patient's height and weight will be measured and recorded using a scale already located in the practice site clinic.

- **Group 2 (Intervention)** – Patients are prescribed CAM boot as part of their standard of care treatment and provided nutritional/exercise information at the time the CAM boot is dispensed.

Patients will be provided upper body physical exercises consisting of seated upper body physical exercises (with or without weights) to include chest press, chest pulls, butterfly wings, front raise, upright row, biceps curls, overhead press and triceps extension exercises (Appendix 1). Patient is instructed to perform these exercises three days per week and each exercise three times per session (or to the best of his/her ability).

Patients will be provided nutritional guidelines (Appendix 2) which is intended as a guide for adults who want to follow a healthful eating pattern.

Patients will also be given a Patient Diary (Appendix 3) to complete their daily meal intake and physical exercises. Use of and return of the diary is optional but encouraged. A dietary scale will also be provided for use throughout the study for weighing food if participants are interested. This is also an optional component of the study. It has been found that use of a patient diary to record food intake and a dietary scale to weigh food helps teach portion control and keeps one from eating more than they planned. They can be useful tools in weight control.

Patients will also be given an Albumin lab test request for blood (8mL) to be drawn at the PSHMC Clinical Laboratories at time of enrollment (+/- 5 days) and again at their final visit (+/- 5 days). Patients with abnormal lab testing results will be referred to their primary care physician for further evaluation and management.

Patient's height and weight will be measured and recorded using a scale already located in the practice site clinic.

7.2.2 Visit 2 – Final Follow-Up Visit

Patients will return to the clinic site for their standard of care visit. At their final visit (when CAM boot use is no longer required), the following will occur:

- **Group 1 (Control):** Patient will be given an Albumin lab test request for blood (8mL) to be drawn at the PSHMC Clinical Laboratories at time of the final study visit. The blood draw

must occur within 5 days of the final visit. Final height and weight will be measured and recorded using a scale located in the practice site clinic.

- Group 2 (Intervention): Final height and weight will be measured and recorded using a scale located in the practice site clinic. Patient will be given an Albumin lab test request for blood (8mL) to be drawn at the PSHMC Clinical Laboratories at time of the final study visit. The blood draw must occur within 5 days of the final visit. Patient will complete the Participant Survey. The dietary scale is to be returned at this visit. Return of the Patient Diary is optional.

	Control	Intervention	
Visit 1 (Enrollment)	Albumin level (bloodwork)	Albumin level (bloodwork)	
	Weight	Weight	
	Height	Height	Patient Diary provided to patient
			Nutritional/Exercise Guidelines provided to patient
			Dietary Scale provided to patient
	Control	Intervention	
Visit 2 (Final Visit)	Albumin level (bloodwork)	Albumin level (bloodwork)	
	Weight	Weight	
	Height	Height	Participant Survey
			Dietary Scale returned
			Patient Diary returned (optional)

7.3 Duration of Participation

Patients will be enrolled in the study from time the CAM boot is dispensed until they no longer need to wear the CAM boot. The patient will be seen a total of two times (enrollment and final follow-up visit).

8.0 Data and Specimen Banking For Future Undetermined Research

N/A

9.0 Statistical Plan

9.1 Sample size determination

Approximately 50 patients will take part in this research study – 25 patients will make up the intervention group (nutritional/exercise information) group and an additional 25 will make up the control group.

We expect the change in weight from baseline to of CAM boot removal + no nutritional information group to increase by 10 lbs. and to remain unchanged (i.e., 0 lbs.) in the CAM boot + nutritional information group. Further, we assume the standard deviation for the change in weight form baseline to time of CAM boot removal will be 12 lbs. Based on these assumptions, a sample size of 25 per group will provide 82% power to detect a difference in the change in weight between the two groups of 10 lbs. using a two-sided test having a significance level if 0.05.

9.2 Statistical methods

Baseline characteristics between the two groups (CAM boot + no nutritional information and CAM boot + nutritional information) will be compared using a chi-square test for categorical variables (e.g., sex) and a two-sample t-test for continuous variables (e.g., the primary of the change in weight from baseline to

CAM boot removal). In the event a continuous outcome is not normally distributed, the nonparametric Wilcoxon Mann Whitney test will be used rather the two-sample t-test.

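### Section 9.2 leaves baseline weight out of the primary comparison; adding it by regression is a cheap improvement to a valid test, with a gain that is possible but not assured

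*Combined protocol and SAP*

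**What the plan says.** Section 9.2 opens with the comparison of baseline characteristics. Its parenthesis, however, assigns the primary outcome to the same method, a "two-sample t-test for continuous variables (e.g., the primary of the change in weight from baseline to" boot removal. The fallback is also unadjusted: "In the event a continuous outcome is not normally distributed, the nonparametric Wilcoxon Mann Whitney test will be used" instead. Neither section 9.2 nor any other section mentions regression, analysis of covariance or another adjustment for baseline. Section 9.2 names tests but no effect estimate or confidence interval.

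Section 9.1 rests on the same unadjusted comparison. It states that "a sample size of 25 per group will provide 82% power to detect a difference in the change in weight between the two groups"; the target difference there is 10 lb and the test is two-sided at 0.05. For the spread it says "we assume the standard deviation for the change in weight form baseline to time of CAM boot removal will be 12 lbs".

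The covariate is collected in any case. Section 3.1 requires "Participants willing to have weight measured at the clinic site at time of enrollment and at final visit". Section 7.2.1 says for each arm that "Patient's height and weight will be measured and recorded using a scale already located in the practice site clinic", and section 7.2.2 says for each arm that "Final height and weight will be measured and recorded using a scale located in the practice site clinic". Section 7.1 describes a randomised trial with two groups.

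**The concern.** With 25 patients per arm, the groups can differ in mean baseline weight by chance. If weight change is related to baseline weight, part of the 12 lb SD is explainable, and an unadjusted comparison leaves that part in the error. Regression on baseline weight would take it out using a measurement the trial already has. The choice has to be written down in advance, because a decision to adjust made after seeing the baseline table would be open to challenge.

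At stake is the precision of the estimated difference in pounds. The correctness of the planned test is not in question.

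**Working it through.** **Inputs.** From section 9.1: 25 per arm, difference 10 lb, SD of change 12 lb, two-sided 0.05. Not in the documents, so assumed over a range: r, the within-arm correlation of baseline weight with weight change.

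**Step 1: reproduce the plan's figure.** SE = 12 × √(2/25) = 3.394 lb. Noncentrality = 10/3.394 = 2.946. The noncentral t with 48 degrees of freedom gives power 82.3%, which matches the stated 82%. Sections 9.1 and 9.2 agree with each other.

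**Step 2: check that the planned test is valid.** In 40,000 simulated trials per setting, at r = 0, 0.3 and 0.5, the t-test on change had type I error 4.96%, 4.89% and 5.02%. Its mean estimate was 9.98, 10.00 and 10.01 lb for a true 10 lb. Leaving out baseline weight causes neither bias nor an inflated error rate.

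**Step 3: add baseline weight.** Regressing final weight on arm and baseline weight gives the same arm coefficient as regressing weight change on them, so the quantity estimated is still the difference in mean change. The residual SD is 12 × √(1 − r²). One degree of freedom is used, leaving 47. The variance is inflated by 1 + 1/46 because the slope is estimated:

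SE = √[144 × (1 − r²) × (2/25) × (1 + 1/46)]

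| Assumed \|r\| | SE (lb) | 10/SE | Power |
|---|---|---|---|
| Unadjusted | 3.394 | 2.946 | 82.3% |
| 0 | 3.431 | 2.915 | 81.5% |
| 0.10 | 3.414 | 2.929 | 81.8% |
| 0.15 | 3.392 | 2.948 | 82.3% |
| 0.20 | 3.361 | 2.975 | 83.0% |
| 0.30 | 3.273 | 3.055 | 84.9% |
| 0.50 | 2.971 | 3.366 | 90.9% |

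Break-even in power is at |r| of about 0.149 (r² about 0.022). At r = 0 power falls from 82.30% to 81.45%, a loss of 0.85 points. Simulation agrees: regression power was 81.3%, 85.1% and 91.1% at r = 0, 0.3 and 0.5, with type I error 5.02%, 4.93% and 5.08%.

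**Step 4: which r is plausible?** Assume weight has the same SD, S, before and after, with correlation ρ. Then 144 = 2S²(1 − ρ), so 1 − ρ = 72/S². The covariance of change with baseline is −S²(1 − ρ) = −72, so |r| = 72/(12 × S) = 6/S.

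| Assumed S (lb) | \|r\| | Power, adjusted |
|---|---|---|
| 12 | 0.50 | 90.9% |
| 20 | 0.30 | 84.9% |
| 40 | 0.15 | 82.3% |
| 60 | 0.10 | 81.8% |

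Equal variance is itself an assumption, and r is sensitive to it. Take S = 40 lb and a final SD of 38 lb. The covariance of the two weights is (1600 + 1444 − 144)/2 = 1450, and r = (1450 − 1600)/(40 × 12) = −0.31, close to the 0.30 row. With a final SD of 42 lb the covariance is (1600 + 1764 − 144)/2 = 1610, and r = 10/480 = 0.02, close to the zero row.

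**Step 5: chance imbalance.** A baseline difference of z standard errors moves the unadjusted estimate by |r| × 3.394 × |z| lb. The average |z| is √(2/π) = 0.798, so the average shift is 0.15 × 3.394 × 0.798 = 0.41 lb at |r| = 0.15 and 0.81 lb at |r| = 0.3. This is not a second benefit. At |r| = 0.3 the shift has SD 0.3 × 3.394 = 1.02 lb and the remainder √0.91 × 3.394 = 3.24 lb, and √(1.02² + 3.24²) = 3.39 lb, the unadjusted SE. The t-test's standard error already contains the imbalance.

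**The case against.** The strongest reply is that this is a preference. The planned test is fixed in advance, unbiased under randomisation and consistent with section 9.1, and no stratification factor is described that would call for adjustment. All of that stands, and it limits the point to a suggested improvement.

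The second reply is that the gain rests on an unsupported correlation. Sections 3.1 and 3.2 admit both sexes from age 18 with no weight limit. A baseline SD of 12 lb, which |r| = 0.5 needs under equal variances, is therefore hard to defend, and so to a lesser degree is 20 lb for |r| = 0.3. This also stands. The 90.9% figure should not be used to argue for the change. What remains is the asymmetry: the loss cannot exceed about 0.9 points, while at |r| = 0.3 the gain is 84.9 − 82.3 = 2.6 points, and step 4 shows that a modest departure from equal variances is enough to reach about that value.

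The third reply is that a regression as primary analysis should not displace the plan's provision for non-normal data. The fix therefore keeps the t-test or Wilcoxon comparison as a supporting analysis. Whether a normality check should choose between them is a separate question.

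A reader might infer that the unadjusted test is biased, that the trial is underpowered without adjustment, or that chance imbalance is a harm over and above the stated standard error. The documents support none of these: allocation is randomised, the 82% reproduces, and step 5 shows the imbalance is already counted.

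**Conclusion.** The point holds as an inexpensive improvement and not as an error in the plan. Section 9.2 does not use a baseline measurement that both arms supply, and no other section makes up for it. Relative to 82.3% and 3.39 lb unadjusted, adjustment changes power by −0.9, 0 and +2.6 points and gives an SE of 3.43, 3.39 and 3.27 lb at assumed |r| of 0, 0.15 and 0.3. Under equal variances, a baseline SD of about 40 lb or more brings no power gain. These figures rest on section 9.1's own 10 lb and 12 lb, on 25 analysed per arm, and on a linear relation with normal errors. The documents fix neither r nor the baseline SD, so the direction of the net effect is uncertain, although the loss is small and bounded. The sample size need not change on this account.

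**What to change.** In section 9.2, separate the primary analysis from the baseline comparisons and state, for example: *The primary analysis is a linear regression of weight at CAM boot removal on treatment arm and baseline weight. The adjusted mean difference in lb, with its 95% confidence interval, is the primary result. The unadjusted comparison of weight change (two-sample t-test, or Wilcoxon Mann Whitney if the outcome is not normally distributed) is a supporting analysis.*

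This also gives the plan a stated estimate and interval on the scale of section 9.1. It should be settled before outcome data are seen.

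The cost is wording only, with no new visit or measurement. One degree of freedom is used, which costs at most about 0.9 power points if baseline weight turns out to be unrelated to weight change.
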